**[Time Frame: Baseline and post-intervention]**

#### **4. Statistical Analysis Plan (SAP)**

The statistical analysis will be performed using IBM SPSS Statistics version 27. The study was conducted on breast cancer survivors aged 35 - 45 years undergoing or recently completing radiation therapy. The primary objective of the study was to compare the effects of two intervention protocols between Group A (MMV – Multimodal Exercise with Verbal Cues) and Group B (MMWV – Multimodal Exercise without Verbal Cues) on shoulder joint range of motion, fatigue, and salivary cortisol levels.

##### **4.1 Primary Outcome**

The primary outcome measures included shoulder range of motion, specifically shoulder flexion, shoulder abduction, and external rotation, measured using a goniometer.

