### **3. Study Protocol**

#### **3.1 Research Design Outline**

The study was conducted as a completed clinical trial among breast cancer survivors undergoing radiation therapy at Saveetha Medical College and Hospital.

Initially titled “Impact of Verbal Cueing in Multimodal Exercise Rehabilitation: A Retrospective Study in Breast Cancer Survivors Undergoing Radiation Therapy,” the trial successfully evaluated the effectiveness of a multimodal exercise rehabilitation program delivered with verbal cueing compared to the same program delivered without verbal cueing.

Participants who were undergoing radiation therapy were allocated into two groups: one group received the multimodal exercise program accompanied by structured verbal cues, while the comparison group performed the same exercise program without verbal guidance. Upon completion of the intervention period, outcomes were assessed to determine the impact of verbal cueing on physical and physiological parameters.

The outcome measures included shoulder range of motion, cancer-related fatigue, and

physiological stress levels. Shoulder range of motion was measured using a universal goniometer for shoulder flexion, abduction, and external rotation. Cancer-related fatigue was evaluated using the FACIT–Fatigue scale, and physiological stress was assessed through salivary cortisol analysis.

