## **Assessment & Outcomes Measures**

### **3.1.1 Primary outcomes**

#### **Shoulder Range of Motion (ROM)**

Shoulder range of motion was evaluated as a primary functional outcome measure, with particular emphasis on shoulder flexion, abduction, and external (lateral) rotation of the affected upper limb. These movements are critical for performing overhead activities, self-care tasks, and functional reaching, and are commonly restricted in breast cancer survivors due to radiation-induced fibrosis, post-surgical scarring, pain, and muscle tightness.

Active ROM was measured using a standard universal goniometer, following established anatomical landmarks and standardized testing positions to ensure accuracy and reproducibility. Assessments were conducted at baseline prior to the initiation of the exercise intervention and repeated at the end of the intervention period.

Improvements in shoulder flexion, abduction, and external rotation following the intervention indicate enhanced joint mobility, improved soft-tissue extensibility, and better functional use of the upper limb. Goniometric assessment of shoulder ROM is widely accepted in clinical and research settings and has demonstrated high intrarater and interrater reliability, making it a valid and responsive tool for evaluating changes in shoulder function in oncological rehabilitation populations.

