##### **4.2 Secondary outcome**

The secondary outcome measures were fatigue, assessed using the Functional Assessment of Chronic Illness Therapy–Fatigue (FACT-F) scale, and salivary cortisol levels, measured in ng/mL.

A total of 36 participants were included in the study and were equally allocated into two groups, with 18 participants in Group A and 18 participants in Group B. Descriptive statistics were expressed as mean  $\pm$  standard deviation (SD). Inferential statistical analysis will include tests of normality, homogeneity of variance, paired sample t-tests for within-group comparisons, and independent sample t-tests for between-group comparisons. The level of statistical significance was set at  $p < 0.05$ .

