##### **4.3 Missing Data**

For breast cancer survivors who did not attend the scheduled assessment sessions, mean imputation of the corresponding outcome scores from their respective intervention group was applied to

manage missing data.

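### Three shoulder movements are primary at a single 0.05 level with no success rule; counting any one significant movement as success carries a 7% to 13% false-positive chance

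*Combined protocol and SAP*

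**What the plan says.** The protocol's primary-outcome section (3.1.1) describes shoulder range of motion "with particular emphasis on shoulder flexion, abduction, and external (lateral) rotation of the affected upper limb". SAP 4.1 repeats the three movements: "The primary outcome measures included shoulder range of motion, specifically shoulder flexion, shoulder abduction, and external rotation, measured using a goniometer". Neither section ranks them or combines them.

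The tests appear in SAP 4.2, among them "paired sample t-tests for within-group comparisons" and "independent sample t-tests for between-group comparisons". One threshold follows: "The level of statistical significance was set at" p < 0.05. The tests are not assigned to outcomes and sidedness is not given. There are 36 participants, 18 per group.

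SAP 4.2 places the other outcomes below range of motion ("The secondary outcome measures were fatigue", together with salivary cortisol). The opening paragraph of SAP section 4, however, puts range of motion, fatigue and cortisol together in the primary objective. SAP 4.3 says that for missed assessments "mean imputation of the corresponding outcome scores from their respective intervention group was applied". The table of contents gives the SAP three subsections, 4.1 to 4.3. All three are available, and none contains a multiplicity or success rule.

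**The concern.** With three co-listed primary measures and one threshold, the plan does not say whether success needs one movement, a particular movement or all three. The natural reading is one between-group test per movement, though this is inferred. On that reading, any single significant movement can be reported as a primary success, and three chances at 5% give a false-positive rate above 5%. Protocol 3.1 makes the timing matter: "The study was conducted as a completed clinical trial among breast cancer survivors undergoing radiation therapy". A rule left open until now can be chosen to suit the p-values.

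**Working it through.** **Inputs from the documents.** Three primary movements (3.1.1, SAP 4.1); independent-sample t-tests at 0.05, 18 per arm (SAP 4.2), so 34 degrees of freedom; group-mean imputation (SAP 4.3). The plan gives no overall error rate or power figure to reproduce.

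**Assumptions.** One two-sided test per movement; normal outcomes; no true difference in any movement; equal correlation ρ between movements, from 0.5 to 0.95. The documents give no correlations. The results apply equally to post-intervention and change scores, since the plan does not say which is tested.

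**Step 1: upper limit, independent movements.** Either direction: 1 − 0.95³ = 14.3%. Favouring cueing only: 1 − 0.975³ = 7.3%. Independence is unlikely for three movements of one shoulder.

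**Step 2: correlated movements.** Simulated pooled t-tests, 18 per arm, 400,000 runs per setting. Holm's any-one rate here is the chance that the smallest p-value is at or below 0.05/3 = 0.0167.

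| ρ | Any one significant (nominal 5%) | Any one favouring cueing (nominal 2.5%) | At least one after Holm |
|---|---|---|---|
| 0.5 | 12.6% | 6.3% | 4.5% |
| 0.7 | 11.0% | 5.6% | 4.0% |
| 0.8 | 10.0% | 5.0% | 3.6% |
| 0.9 | 8.5% | 4.3% | 3.0% |
| 0.95 | 7.3% | 3.7% | 2.6% |

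Exact integration of the trivariate normal agrees: 12.5% at ρ = 0.5 and 7.3% at ρ = 0.95, either direction.

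**Step 3: does Holm hold under SAP 4.3?** Holm needs each t-test to hold its own level. Let m participants per arm be imputed at their group mean, with k = 18 − m measured. Imputed values add nothing to the sum of squares but are counted as observed, so the t statistic is too large by the factor √[(34 × 18)/((2k − 2) × k)]. The null rejection rate is the chance that a t variable on 2k − 2 degrees of freedom exceeds 2.032 divided by that factor, in either direction. The documents do not say how many scores were missing, so m is assumed.

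| m per arm | Factor | Effective cut-off | Single-test rejection | Holm any-one, ρ = 0.5 to 0.95 |
|---|---|---|---|---|
| 1 | √(612/544) = 1.061 | 1.916 | 6.4% | 6.3% to 3.6% |
| 2 | √(612/480) = 1.129 | 1.800 | 8.2% | 8.7% to 5.1% |
| 3 | √(612/420) = 1.207 | 1.684 | 10.3% | 11.7% to 6.9% |

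On measured scores only, with 16 per arm, Holm's any-one rate is 4.5% to 2.7%. Adjustment alone is therefore not enough if the imputed values stay in the primary tests.

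**Step 4: power.** Noncentral t, assumed difference 1.0 SD, noncentrality √(n/2).
- n = 18 (noncentrality 3.0): 83% at 0.05 and 68% at 0.0167.
- n = 16 (noncentrality 2.83): 78% at 0.05 and 62% at 0.0167.
- Difference detectable with 80% power at n = 18: 0.96 SD at 0.05 and 1.13 SD at 0.0167.

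**The case against.** The any-one rule is not in the plan. If each movement is reported as its own comparison, each test holds 5% on complete data. If all three must be significant, there is no inflation. This is correct, and the 13% to 7% is conditional on the permissive reading. It does not rescue the plan, because the plan states neither of the stricter readings and excludes none of the permissive ones.

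The harm in the direction of interest is modest: at correlations of about 0.8 or more, the chance of a false result favouring cueing does not exceed 5%. That also stands, although the like-for-like nominal rate is 2.5%.

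Imputation could be called a separate defect. It belongs here because Step 3 shows that Holm does not reliably hold 5% while the imputed values remain.

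Unadjusted 95% intervals may disagree with Holm. At ρ = 0.7 and a true 0.8 SD difference in all three movements (both assumed), about 24% of trials would have an interval excluding zero for a movement that Holm does not pass; under no effect it is about 8%. The answer is that claims follow Holm and the intervals are descriptive.

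The opening of SAP section 4 also gives fatigue and cortisol primary status. Counting them would raise the error further, so the fix must close that route.

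Finally, a rule added to a completed trial is not prespecified control. That is conceded. Its value is in limiting what is claimed.

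**Conclusion.** The concern holds and should be fixed. The firm part is that primary success is undefined across three unranked movements tested at one level. The size depends on stated assumptions: one two-sided test per movement, any one counting as success, complete data, no true effect, and correlations of 0.5 to 0.95. On these, the any-one false-positive rate is about 13% to 7% against 5%, or about 6% to 4% against 2.5% for results favouring cueing. The data are not invalidated; what is affected is the claim that can be drawn from them.

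**What to change.** In SAP 4.1:
- State one between-group test for each movement.
- Apply Holm to the three p-values: smallest against 0.0167, next against 0.025, last against 0.05, stopping at the first failure. Claim an effect only for movements that pass, and name them.
- Report all three between-group differences with 95% confidence intervals whatever the result.
- Run these tests on measured scores, without the SAP 4.3 imputation, and give the number analysed per arm.
- Rest any claim about cueing on the between-group tests, not on the paired tests.
- Report fatigue and cortisol as secondary, with no confirmatory claim, and bring the opening of SAP section 4 into line.
- Date the rule and disclose that it was added after the trial was completed.

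This needs a few sentences and no new data. The cost is power, as in Step 4: 83% to 68% for a 1.0 SD difference in one movement, or 62% with two per arm missing. Using measured scores also assumes that missingness is unrelated to outcome.

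Holm is a choice. The mean of the three standardised movements is an acceptable alternative. At an assumed correlation of 0.7 it has 90% power if all three differ by 1.0 SD (Holm, at least one: 85%), but 19% if only one does (Holm: 69%), and it cannot say which movement changed. For showing an effect in all three, Holm has 67% power and an all-three rule 70%.

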##### **4.2 Secondary outcome**

The secondary outcome measures were fatigue, assessed using the Functional Assessment of Chronic Illness Therapy–Fatigue (FACT-F) scale, and salivary cortisol levels, measured in ng/mL.

A total of 36 participants were included in the study and were equally allocated into two groups, with 18 participants in Group A and 18 participants in Group B. Descriptive statistics were expressed as mean  $\pm$  standard deviation (SD). Inferential statistical analysis will include tests of normality, homogeneity of variance, paired sample t-tests for within-group comparisons, and independent sample t-tests for between-group comparisons. The level of statistical significance was set at  $p < 0.05$ .

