### **Salivary Cortisol Level**

Physiological stress response was evaluated through the measurement of salivary cortisol levels, a non-invasive biomarker that reflects hypothalamic–pituitary–adrenal (HPA) axis activity. Saliva samples were collected under standardized conditions to minimize the effects of diurnal variation in cortisol secretion.

Samples were obtained at consistent times of the day at baseline and after completion of the intervention period to ensure comparability of results.

Elevated salivary cortisol levels are commonly associated with chronic stress, fatigue, and altered neuroendocrine regulation in breast cancer survivors undergoing radiation therapy. A reduction or normalization of cortisol levels following the intervention indicates improved stress regulation, enhanced autonomic balance, and better physiological adaptation to treatment-related stress.

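### Salivary cortisol is tested in ng/mL with no stated scale, no baseline covariate and a normality test that leads nowhere; this can cost power, by an amount that depends on the unknown distribution.

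*Combined protocol and SAP*

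**What the plan says.** Section 4.2 of the SAP makes cortisol a secondary outcome, "salivary cortisol levels, measured in ng/mL". The opening of section 4 also places it in the primary objective, which is to compare the two programmes "on shoulder joint range of motion, fatigue, and salivary cortisol levels".

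One analysis rule covers every outcome: mean and SD for description, then "tests of normality, homogeneity of variance, paired sample t-tests for within-group comparisons, and independent sample t-tests for between-group comparisons". The groups are small, "with 18 participants in Group A and 18 participants in Group B", and the significance level is 0.05 with sidedness not stated.

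The documents give no transformation, no rank-based alternative, no covariate, and no action if normality or equal variance is rejected. They do not say whether the between-group test uses post-intervention values or changes. The Salivary Cortisol Level section says samples were taken under standard conditions "to minimize the effects of diurnal variation in cortisol secretion". That controls one source of spread but does not settle the shape of the distribution or the scale of analysis.

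**The concern.** Cortisol is a strictly positive concentration, yet it gets the same treatment as a joint angle. The SAP never says that the values are analysed untransformed. That is inferred from the unit and from the absence of any other scale, and it is the only reading that the text supports.

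If the values are strongly right-skewed, one or two high readings among 18 can dominate a group's mean and SD, and a proportional difference becomes harder to detect. A normality test with no stated consequence leaves two possibilities: the t-test is run regardless, or the analyst chooses an alternative after seeing the data. Baseline cortisol is collected in everyone but is not used to sharpen the between-group comparison. What is at stake is power and precision on the trial's only biomarker.

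**Working it through.** **No figure to reproduce.** The documents state 36 participants but give no power, effect size, SD or CV for any outcome. The power figures below are therefore conditional.

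**Inputs from section 4.2:** 18 per group, alpha 0.05, independent-sample t-test. **Assumed:** two-sided test, complete data, a proportional treatment effect, baseline–post correlation 0.5, CV from 30% to 100%.

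**Reference effect.** 80% power with 18 per group needs a standardised difference of d = 0.96. The non-centrality is 0.96 × √(18/2) = 2.88, against a critical t of 2.03 on 34 df. This d is set on the log scale, so the log t-test on post values has 80% power by construction. At correlation 0.5 the SD of a log change is σ√(2(1 − 0.5)) = σ, so the log-change t-test also has 80%. Adjusting for log baseline shrinks the residual SD by √(1 − 0.5²) = 0.866. The effective d becomes 0.96/0.866 = 1.11, and power rises to 89%.

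**Log-normal cortisol.** σ = √(ln(1 + CV²)), and the between-group ratio is exp(−0.96σ). Simulated power of the analyses in ng/mL (repeat runs agree to about one point):

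| CV | σ | Ratio | Post values (log: 80%) | Changes (log: 80%) | Baseline-adjusted (log: 89%) |
|---|---|---|---|---|---|
| 30% | 0.29 | 0.75 | 78% | 71% | 87% |
| 50% | 0.47 | 0.64 | 76% | 62% | 84% |
| 75% | 0.67 | 0.53 | 71% | 52% | 79% |
| 100% | 0.83 | 0.45 | 67% | 44% | 74% |

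The loss for post values is 80 − 78 = 2, then 4, 9 and 13 points. For changes it runs from 80 − 71 = 9 to 80 − 44 = 36 points. With no true difference, rejection rates stay between about 4% and 5%.

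**Gamma-shaped cortisol.** This is also positive and right-skewed. With the effect again set for about 80% power on the log scale, ng/mL against log gives:

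- post values: 84% v 80% at CV 50%, 91% v 81% at CV 100%;
- baseline-adjusted: 91% v 89% at CV 50%, 94% v 88% at CV 100%;
- changes: 70% v 80% at CV 50%, so untransformed changes lose here too.

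**The proposed analysis against the t-test on untransformed post values, gamma skew, fixed ratios:**

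| CV | Ratio | Log, baseline-adjusted | Post values in ng/mL |
|---|---|---|---|
| 30% | 0.75 | 87% | 80% |
| 50% | 0.60 | 89% | 83% |
| 71% | 0.60 | 57% | 53% |
| 100% | 0.45 | 56% | 58% |

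**The normality test as a guide.** For log-normal data, Shapiro-Wilk at n = 18 rejects in about 20%, 42%, 66% and 80% of samples at CV 30%, 50%, 75% and 100%. Even so, a rule that switches to logs when either group is rejected had about the same power (roughly 80%) as always using logs.

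**The case against.** The strongest objection is that log-normal data are the case for which logs are ideal, and the documents do not show that cortisol has that shape. This stands. A reader might infer that power is lost whenever concentrations are right-skewed, or that the log scale is simply the better method. Neither follows: under gamma skew the untransformed scale does as well or better, both for post values and with baseline adjustment.

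Second, the larger losses for post values need a CV of 75% to 100%. At d = 0.96 those settings imply ratios of about 0.53 and 0.45, that is, 47% to 55% lower cortisol from adding verbal cues to the same exercise programme. At CV 30% the loss is about 2 points. This also stands.

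Third, the largest losses apply only if changes are compared, and section 4.2 does not say so. That is correct, but the omission is itself part of the gap.

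Fourth, most of the dependable gain comes from the covariate and not from the transformation. This stands and is reflected in the verdict.

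Fifth, weak detection by the normality test does not show a loss of power, because the switching rule performs about as well. This stands. The reason to fix the scale beforehand is to avoid a data-driven choice.

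Last, cortisol is secondary, and sections 3.1.1 and 4.1 name only shoulder range of motion as primary. The primary range-of-motion comparison is untouched. The mention of cortisol in the primary objective raises its prominence but does not make it a primary outcome.

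**Conclusion.** The specification gap is certain from the text: no scale is stated, baseline is not used as a covariate, the choice between post values and changes is left open, and the normality test has no consequence. The size of the harm is conditional. If cortisol is log-normal, the t-test on untransformed post values gives up about 2 to 13 points of power over CV 30% to 100%, and the t-test on untransformed changes about 9 to 36 points. If the skew is gamma-like, untransformed post values give up nothing. These figures rest on an assumed shape, CV, proportional effect and correlation of 0.5.

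A reader might suspect excess false positives. The simulations do not support that: Type I error stays at or slightly below 5% under log-normal skew.

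The change is still worth making. The log-scale baseline-adjusted analysis beats the t-test on untransformed changes under both shapes. It also beats the t-test on untransformed post values except under strong gamma skew. This is an inexpensive improvement to a secondary analysis and does not threaten the trial's main conclusion.

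**What to change.** Add to section 4.2:

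> Groups will be compared on log-transformed post-intervention salivary cortisol, with log-transformed baseline cortisol as a covariate. The result will be reported as a ratio of geometric means with a 95% CI. A baseline-adjusted analysis in ng/mL will be a sensitivity analysis. The scale will not be chosen from the normality test.

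Describe cortisol by geometric mean and by median with interquartile range. State in section 4.3 whether the group-mean imputation for cortisol is done on the log or the ng/mL scale.

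Section 3.1 describes the trial as completed, while section 4 puts the analysis in the future tense. If outcome data have already been seen, the change should be dated and labelled post hoc.

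The cost is a few sentences and the log-transformed cortisol variables in SPSS. There are two downsides. The effect becomes a ratio and not a difference in ng/mL. Some power may also be lost if the skew is gamma-like: 88% against 94% for the baseline-adjusted analysis in ng/mL at CV 100%. The sensitivity analysis keeps that comparison in view.

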### **3.3 Recruitment**

All breast cancer survivors undergoing radiation therapy and attending the study setting were enrolled in the clinical trial after meeting the eligibility criteria. Participant information sheets and informed consent forms were provided to all eligible individuals, detailing the purpose of the study, intervention procedures, and inclusion and exclusion criteria. Participants who consented to participate were enrolled in the trial and underwent baseline assessments prior to the initiation of the intervention.

Baseline evaluations included assessment of shoulder range of motion using a universal goniometer, cancer-related fatigue assessment using the FACIT–Fatigue scale, and evaluation of physiological stress through salivary cortisol analysis. Written informed consent was obtained from all participants, and signed consent forms were collected and retained by the site principal investigator before the commencement of any study-related procedures.

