### **3.1.2 Secondary outcomes**

Cancer-related fatigue was assessed using the Functional Assessment of Chronic Illness Therapy–Fatigue (FACIT–F) Scale, a validated, self-administered questionnaire specifically developed to evaluate fatigue

and its impact on daily functioning in individuals with chronic illnesses, including cancer. The FACIT–F consists of 13 items rated on a 5-point Likert scale ranging from 0 (“not at all”) to 4 (“very much”), with total scores ranging from 0 to 52.

- o Higher FACIT–F scores indicate lower levels of fatigue and better functional well-being. Participants completed the questionnaire at baseline and after completion of the intervention period.
- o Cancer-related fatigue is one of the most common and persistent symptoms experienced by breast cancer survivors undergoing radiation therapy and can markedly affect physical performance, emotional health, and overall quality of life. The FACIT–Fatigue Scale has demonstrated excellent reliability, validity, and sensitivity to change in oncology populations, making it an appropriate and responsive outcome measure for evaluating the effectiveness of exercise-based rehabilitation interventions.

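### The between-group t-tests name neither the analysed variable nor a baseline covariate; ANCOVA on the baseline already collected would be the more precise primary analysis over most plausible correlations

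*Combined protocol and SAP*

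**What the plan says.** After preliminary checks of normality and equal variances, SAP section 4.2 lists "paired sample t-tests for within-group comparisons, and independent sample t-tests for between-group comparisons". The sentence stands under the secondary-outcome heading, but no other test appears in the SAP. It has to be read as covering the primary range-of-motion outcomes too, because the stated primary objective is the comparison of the two groups.

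Baseline values exist for every outcome:
- Recruitment section: participants "underwent baseline assessments prior to the initiation of the intervention".
- Range of motion: "Assessments were conducted at baseline prior to the initiation of the exercise intervention and repeated at the end of the intervention period".
- FACIT-Fatigue: "Participants completed the questionnaire at baseline and after completion of the intervention period".
- Salivary cortisol: "Samples were obtained at consistent times of the day at baseline and after completion of the intervention period".

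On size, section 4.2 states: "A total of 36 participants were included in the study and were equally allocated into two groups", 18 in each. On allocation, section 3.1 says only: "Participants who were undergoing radiation therapy were allocated into two groups". The text available for this review, from which a few pages had been removed, does not mention randomisation.

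**The concern.** There are two separate problems.

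**The analysed variable is undefined.** A t-test on post values and a t-test on change scores both fit the wording. They can give different verdicts on the same data, and nothing in the plan prevents the choice being made after both have been seen.

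**The baseline is used badly or not at all.** A post-value test ignores it. A change-score test uses it with the slope fixed at 1, which is efficient only when the true slope of post on baseline is near 1; with equal SDs, that means a very high correlation. With 18 per group, avoidable loss of precision matters.

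If allocation was random, either t-test is valid and the second problem costs precision only. If it was not, a systematic baseline difference biases the post-value test, and may bias the change-score test depending on how the difference arose.

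**Working it through.** The plan gives no sample-size calculation, SD, effect size or power, so there is no figure of its own to reproduce.

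**Inputs.** From SAP section 4.2: 18 per group and a 0.05 significance level. Assumed: two-sided testing; equal baseline and post SDs (set to 1); a common slope; baseline-post correlation r of 0.3, 0.5 and 0.7, with 0.8 and 0.9 added for precision; and an illustrative effect of 0.7 SD.

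**Variance.** The variance of the estimated group difference is V × 2/18, where
- post values: V = 1
- change scores: V = 2(1 − r)
- ANCOVA: V = (1 − r²) × 33/32. The factor 33/32 = 1 + 1/(2×18 − 4) is the small-sample cost of estimating the slope.

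At r = 0.5, for example, change gives 2 × 0.5 = 1.00 and ANCOVA gives 0.75 × 33/32 = 0.773.

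| r | V change | V ANCOVA | ANCOVA / post | ANCOVA / change |
|---|---|---|---|---|
| 0.3 | 1.40 | 0.938 | 94% | 67% |
| 0.5 | 1.00 | 0.773 | 77% | 77% |
| 0.7 | 0.60 | 0.526 | 53% | 88% |
| 0.8 | 0.40 | 0.371 | 37% | 93% |
| 0.9 | 0.20 | 0.196 | 20% | 98% |

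**Break-even.** Setting (1 − r²) × 33/32 = 1 gives r = √(1/33) = 0.17. Setting (1 + r)/2 × 33/32 = 1 gives r = 64/33 − 1 = 0.94. Allowing for the lost degree of freedom, ANCOVA is the most precise of the three from about 0.18 to 0.93. Outside that range its loss is at most about 3% of variance (V = 1.03 against 1 for post values at r = 0).

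**Detectable difference and power** (non-central t; 34 df for the t-tests, 33 for ANCOVA):

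| r | 80%-power difference in SD: post / change / ANCOVA | Power at 0.7 SD: post / change / ANCOVA |
|---|---|---|
| 0.3 | 0.96 / 1.14 / 0.93 | 53% / 41% / 56% |
| 0.5 | 0.96 / 0.96 / 0.85 | 53% / 53% / 64% |
| 0.7 | 0.96 / 0.74 / 0.70 | 53% / 75% / 80% |

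**Effect of the undefined variable** (40,000 simulated trials per scenario, bivariate normal, random allocation). With a true 0.7 SD effect, the post-value and change-score tests disagree on significance in 32.0%, 33.6% and 38.8% of trials at r = 0.3, 0.5 and 0.7. With no effect, each holds 5%, but at least one is significant in about 9%.

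**If allocation was not random** (illustration only: an assumed systematic baseline gap of 0.5 SD, no effect, r = 0.5 / 0.7):
- If groups equal at baseline would end equal, the bias is r × 0.5 = 0.25 / 0.35 SD for post values, (r − 1) × 0.5 = −0.25 / −0.15 for change, and 0 for ANCOVA.
- If the gap is a stable true difference, the bias is 0.50 for post values, 0 for change, and (1 − r) × 0.5 = 0.25 / 0.15 for ANCOVA.

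**The case against.** Five points can be made against this.

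1. **Equal SDs are assumed.** With k the ratio of baseline to post SD, the change-score factor is k² + 1 − 2rk, while ANCOVA's does not depend on k. At k = 0.8 and r = 0.7, change gives 0.64 + 1 − 1.12 = 0.520 against 0.526 for ANCOVA; at k = 0.7 and r = 0.7, 0.510 against 0.526. This is correct, so ANCOVA is not always the most precise. But the reversals are about 1% to 3% of variance, whereas at k = 1.3 and r = 0.7 the comparison is 0.87 against 0.526 in ANCOVA's favour.

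2. **The gain is uneven.** It is small over post values at r = 0.3 and small over change scores at r = 0.8 or above. This stands. The gain over both at once is material only in the middle of the range.

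3. **Discordance does not argue for ANCOVA.** Naming either variable in advance would close that gap. ANCOVA and the post-value test themselves disagree in about 10%, 19% and 32% of simulated trials at r = 0.3, 0.5 and 0.7 (0.7 SD effect). This also stands: the discordance supports specification, and the precision results support ANCOVA.

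4. **The 9% is a worst case.** It requires someone to try both tests and report the favourable one, and nothing in the documents suggests this was done. Agreed; the point is that the plan does not rule it out.

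5. **It may be too late.** Section 3.1 states: "The study was conducted as a completed clinical trial". Section 4.2, however, still puts the inferential analysis in the future tense. Timing affects how the change must be disclosed, not whether it is useful.

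**Conclusion.** The concern holds. The between-group analysis that serves the primary objective is not defined, and neither version that fits the wording makes efficient use of a baseline that has already been collected.

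ANCOVA's advantage depends on the unknown correlation: against the better of the two t-tests, it lowers the detectable difference by 0.03 SD at r = 0.3 (0.96 to 0.93), by 0.11 SD at r = 0.5 (0.96 to 0.85) and by 0.04 SD at r = 0.7 (0.74 to 0.70). Against the worse one the reduction is 0.21, 0.11 and 0.26 SD. Where ANCOVA loses under equal SDs, the loss is at most about 3% of variance, so it is the low-risk choice when the correlation is unknown.

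These sizes rest on equal SDs, assumed correlations and groups comparable at baseline. The gain will be smaller if post values are filled with group means (section 4.3), since those carry no individual baseline information; the amount of missing data is not given, so this cannot be quantified. The point should be fixed, but under random allocation it does not make the planned tests invalid.

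**What to change.** - For each outcome, make the between-group analysis an ANCOVA of the post-intervention value on group and the baseline value of the same outcome. Report the adjusted mean difference with its 95% CI.
- Keep the independent t-test as a supporting analysis, and state whether it uses post values or change scores.
- State how participants were allocated. If allocation was not random, present ANCOVA and change-score results side by side, and say that ANCOVA adjusts only for the measured baseline and cannot be relied on to remove all confounding.
- If outcome data have already been seen, make the change as a dated amendment and disclose it as post hoc.

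The cost is a short SAP revision, a standard procedure in the SPSS package already planned, and one degree of freedom. No new data are needed.
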